NCT#: NCT03042468

PROTOCOL # 1609017542
VERSION 6, DATE: 10/28/2021

TITLE: Phase I/II dose-escalation study of fractionated dose $^{177}\text{Lu-PSMA-617}$ for progressive metastatic castration resistant prostate cancer

IRB Protocol #: 1609017542

IND/IDE #: 131966, 124495

Version Date: October 28, 2021 (v.6)

Principal Investigator: [name], M.D., M.S.
[contact]
[contact]
E-mail: [contact]

Participating Sites: Weill Cornell Medicine, Dana Farber Cancer Institute, Tulane Cancer Center

DFCI PI: [name].

Tulane PI: A. [name].

Version 1: August 18, 2016

Version 2: January 11, 2017

Version 3: April 14, 2017

Version 4: May 10, 2018

Version 5: October 1, 2018

Version 6: October 28, 2021

Confidentiality Statement

This document is confidential and is to be distributed for review only to investigators, potential investigators, consultants, study staff, and applicable independent ethics committees or institutional review boards. The contents of this document shall not be disclosed to others without written authorization from WCM.

List of Abbreviations

All abbreviations used throughout the protocol must be defined.

ADT	Androgen Deprivation Therapy
AE	Adverse Event
CRF	Case Report Form
CTC	Circulating Tumor Cells
CTSC	Clinical Translational Science Center
DLT	Dose Limiting Toxicity
DSMB	Data Safety Monitoring Board
DSMP	Data Safety Monitoring Plan
FDA	Food and Drug Administration
HIPAA	Health Insurance Portability and Accountability Act of 1996
ICF	Informed Consent Form
IND	Investigational New Drug
IRB	Institutional Review Board
mAb	Monoclonal Antibody
mCRPC	Metastatic Castration Resistant Prostate Cancer
MTD	Maximum Tolerated Dose
PCa	Prostate Cancer
PSMA	Prostate Specific Membrane Antigen
REDCap	Research Electronic Data Capture
SAE	Serious Adverse Event
WCM	Weill Cornell Medicine

Protocol Summary

Full Title: Phase I/II dose-escalation study of fractionated dose ^{177}Lu -PSMA-617 for progressive metastatic castration resistant prostate cancer

Short Title: Fractionated ^{177}Lu -PSMA-617 for mCRPC

Clinical Phase: Phase I

Principal Investigator: [name], MS

Sample Size: $N = 4 - 63$ (3+3 study design up to 6 dose-escalation cohorts in phase I (up to 36), additional 10-21 in phase II (up to 27 including phase I cohort)

Accrual Ceiling: This study will enroll up to 63 subjects who receive treatment

Study Population: Adult male patients of >18 years age with patients with documented progressive metastatic CRPC

Accrual Period: 3 years

Study Design: Phase I dose escalation study with ^{177}Lu -PSMA-617 using dose fractionation regimen will be performed in patients with documented progressive metastatic CRPC. The cumulative ^{177}Lu dose [**100 mCi (3.7 GBq) – 600 mCi (22.2 GBq)**] will be escalated in up to 6 different dose levels (3 + 3 study design). Additional 10-21 subjects will be enrolled at the MTD/RP2D level in 2-stage design to further assess safety and tolerability and to obtain a preliminary assessment of efficacy.

Study Duration: Primary treatment phase is approximately 3 months after screening

Study Agent/

Intervention Description:

- 1) ^{177}Lu -PSMA-617 [50mCi (1.85GBq) - 300mCi (11.1GBq)] intravenous X2 doses, 2 weeks apart (Visit 1 and 3)
- 2) ^{68}Ga -PSMA-HBED-CC [$5 \pm 2\text{mCi}$ or $185 \pm 74\text{MBq}$] intravenous during screening and at 12 weeks (± 1 week) with standard imaging

Primary Objective:

- Determine the dose limiting toxicity (DLT) of fractionated dose of ^{177}Lu -PSMA-617 (phase I)
- Determine the maximal tolerated and recommended phase II dose of ^{177}Lu -PSMA-617 in a 2-week dose-fractionation regimen (phase I)
- To assess the proportion with PSA decline following treatment with the RP2D of fractionated dose ^{177}Lu -PSMA-617 (Phase II)

Secondary Objectives:

- To assess the rate of PSA decline following fractionated ¹⁷⁷Lu-PSMA-617
 - To assess radiographic response rate by RECIST 1.1 with PCWG3 modifications
 - To assess biochemical and radiographic progression-free survival by PCWG3 criteria
 - To assess overall survival following fractionated ¹⁷⁷Lu-PSMA-617
 - To assess safety of fractionated ¹⁷⁷Lu-PSMA-617 as assessed by CTCAE 4.0
 - To assess changes in CTC count as measured by CellSearch and the rate of favorable CTC count and LDH at 12 weeks following fractionated ¹⁷⁷Lu-PSMA-617
 - To examine whole body distribution of ¹⁷⁷Lu-PSMA-617
 - Estimate radiation dosimetry of ¹⁷⁷Lu-PSMA-617 and correlate toxicity with radiation dosimetry

Exploratory Objectives:

- Disease assessment with ⁶⁸Ga-PSMA-HBED-CC PET/CT prior to and following investigational treatment
- To assess genomic DNA repair pathways in relationship to outcome following fractionated dose ¹⁷⁷Lu-PSMA-617
- To assess patient reported outcomes using FACT-P and the Brief Pain Inventory short form
- To assess the immune effect of ¹⁷⁷Lu-PSMA-617
- To assess reproducibility of ⁶⁸Ga-PSMA-HBED-CC PET/CT

Endpoints:

Dose limiting toxicity (DLT), Adverse event rate, Maximum tolerated dose (MTD), Recommended phase II dose, response rate, progression free survival.

Schema

[figure not shown]

Table of Contents

1. STUDY OBJECTIVES.....	7
1.1 Primary Objectives	7
1.2 Secondary Objectives	7
1.3 Exploratory Objectives.....	7
2. BACKGROUND	8
2.1. Disease.....	8
2.2. PSMA	8
2.3. Radionuclide-chelating PSMA ligands	9
2.3.1. Prior clinical experience with PSMA small molecule(s) in men with prostate cancer: 10	
2.4. Investigational Agent.....	16
2.5. Rationale	17
2.6. Risk/Benefit Assessment	25
2.7. Correlative Studies Background	25
2.7.1. Archival tissue and Cell-Free plasma DNA to assess genomic DNA-repair pathway alterations	25
2.7.2. CTC Count.....	26
2.7.3. PSMA Expression on CTC.....	26
3. SUBJECT SELECTION	27
3.1. Study Population	27
3.2. Inclusion Criteria.....	27
3.3. Exclusion Criteria	28
4. OVERVIEW OF STUDY DESIGN AND METHODOLOGY	29
4.1. Study Design	29
4.2 Rationale for Dose-Escalation Strategy	30
5. REGISTRATION PROCEDURES.....	2
5.1. Identification of subjects	2
5.2. Consent process	3
6. STUDY PROCEDURES	3
6.1. Schedule of Evaluations.....	5
6.1.1. Screening Visit.....	6
6.1.2. Treatment Phase	7
6.2. Treatment Administration.....	11
6.2.1. Agent Administration	11
6.2.2. Study drug preparation	11

6.2.3. Route of Administration	12
6.2.4. Dose levels for ¹⁷⁷ Lu-PSMA-617	12
6.2.5. Dose levels for ⁶⁸ Ga-PSMA-HBED-CC.....	12
6.2.6. Study drug premedication	12
6.2.7. Study drug administration	12

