3.2. Inclusion Criteria

1. Histologically or cytologically confirmed adenocarcinoma of prostate
2. Documented progressive metastatic CRPC based on Prostate Cancer Working Group 3 (PCWG3) criteria, which includes at least one of the following criteria:
 - PSA progression
 - Objective radiographic progression in soft tissue
 - New bone lesions
3. ECOG performance status of 0-2
4. Have serum testosterone < 50 ng/dL. Subjects must continue primary androgen deprivation with an LHRH/GnRH analogue (agonist/antagonist) if they have not undergone orchiectomy.
5. Have previously been treated with at least one of the following in any disease state:
 - Androgen receptor signaling inhibitor (such as enzalutamide)
 - CYP 17 inhibitor (such as abiraterone acetate)
6. Have previously received taxane chemotherapy (in any disease state), been determined to be ineligible for taxane chemotherapy by their physician, or refused taxane chemotherapy.
7. Age ≥ 18 years

8. Patients must have normal organ and marrow function as defined below:

○ Absolute neutrophil count○ Hemoglobin○ Platelet count○ Serum creatinine○ Serum total bilirubin○ Serum AST and ALT	
$\geq 2,000 \text{ cells/mm}^3$ $\geq 9 \text{ g/dL}$ $\geq 150,000 \times 10^9/\mu\text{L}$ $\leq 1.5 \times \text{upper limit of normal (ULN)}$ or calculated creatinine clearance $\geq 60 \text{ mL/min}/1.73 \text{ m}^2$ by Cockcroft-Gault $\leq 1.5 \times \text{ULN}$ (unless due to Gilbert's syndrome in which case direct bilirubin must be normal $\leq 3 \times \text{ULN}$ in absence of liver metastases; $< 5 \times \text{ULN}$ if due to liver metastases (in both circumstances bilirubin must meet entry criteria)

--	---
9. Ability to understand and the willingness to sign a written informed consent document.

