10.2 Biochemical (PSA) response

PSA response will be determined by comparing the PSA levels after therapy to the baseline, pre-treatment PSA. Declines of $\geq 30\%$ confirmed by a second PSA value ≥ 2 weeks later, will be reported. Subjects must not demonstrate clinical or radiographic (CT and/or MR) evidence of disease progression during this time period.

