10.5 PSA Progression

PSA progression will be defined as a rise of $> 25\%$ above either the pretreatment level or the nadir PSA level (whichever is lowest). PSA must increase by > 2 ng/ml to be considered progression. Confirmation requires a second consecutive rising PSA at least 2 weeks apart.

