12.2. Phase II

We will enroll up to 27 subjects into the Phase II portion (including the 3-6 used for establishing the MTD). We will define evaluable patients as patients who met eligibility requirements, have initiated therapy, and were not removed from the study for non-compliance or patient withdrawal.

Sample size recommendations for the two-stage design are determined according to Simon's two-stage minimax design. We project a 30% PSA decline proportion of 35%, below which the regimen will be unacceptable and a 30% PSA decline proportion of 60%, above which the regimen will be considered worthy of further exploration. The null hypothesis that the 30% PSA decline proportion is less than or equal to 35% will be tested against the alternative hypothesis that the 30% PSA decline proportion is greater than or equal to 60%.

The sample size computations were performed assuming a 0.10 one-sided level of significance and 90% power assuming a historical control value for PSA decline of 35% and the alternative hypothesis of 60%. If 6 or fewer of the first 16 evaluable patients do not experience a 30% decline in PSA (stage 1), the study will be terminated and declared to have a negative result. If 7 or more patients out of the first 16 evaluable patients experience a 30% decline in PSA, ongoing accrual will proceed to the target sample size of 27 patients (stage 2). The new regimen will be declared active in this patient population and worthy of further testing if 13 or more patients experience a 30% PSA decline among the 27 patients entered. This two-stage design yields a 0.90 probability of a positive result if the true 30% PSA decline proportion is 60%. It yields a 0.90 probability of a negative result if the true 30% PSA decline proportion is 35%. An exact 95% binomial confidence interval will be constructed for the proportion of patients with PSA decline.

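### The phase II decision rests only on a 30% PSA decline, but no minimum baseline PSA is required; a one-line entry and analysis-set condition would make every counted man assessable

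*Combined protocol and SAP*

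**What the plan says.** The Protocol Summary gives the phase II primary objective as "To assess the proportion with PSA decline following treatment with the RP2D of fractionated dose". Section 12.2 turns this into a two-stage rule on a 30% decline. The null is "We project a 30% PSA decline proportion of 35%, below which the regimen will be unacceptable" and the alternative is "a 30% PSA decline proportion of 60%, above which the regimen will be considered worthy of further exploration", planned "assuming a 0.10 one-sided level of significance and 90% power". The trial goes on to 27 men "If 7 or more patients out of the first 16 evaluable patients experience a 30% decline in PSA", and activity is declared with 13 or more declines among the 27.

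Inclusion criterion 2 in section 3.2 is met by any one of three kinds of progression. One is "Objective radiographic progression in soft tissue"; another is new bone lesions. Neither 3.2 nor 3.3 sets a minimum PSA. PSA is drawn at screening and on Day 1, but no value is required.

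Sections 4.2 and 12.2 define an evaluable man as one who was eligible, started therapy and was not removed for non-compliance or withdrawal. Section 12.7.2 asks in addition for completed treatment and at least 12 weeks of follow-up. None of these mentions baseline PSA.

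Section 10.2 makes response relative: "PSA response will be determined by comparing the PSA levels after therapy to the baseline, pre-treatment PSA". The decline must be at least 30%, be confirmed at least 2 weeks later, and occur without clinical or radiographic progression. It has no absolute floor. Progression does have one: "PSA must increase by > 2 ng/ml to be considered progression" (section 10.5), and 10.3 and 10.7 use the same 2 ng/mL amount.

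**The concern.** A percentage decline can be read only if there is enough PSA to fall. A man who enters on imaging progression with undetectable PSA cannot show a decline whatever his tumour does, yet he stays in the 16 and the 27 as a non-responder. At a very low but measurable PSA the percentage is unstable. At an illustrative 0.3 ng/mL, a fall of 0.1 ng/mL is 0.1/0.3 = 33%, whereas PSA progression would need a rise of more than 2 ng/mL, to above 2.3 ng/mL.

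The sole go/no-go endpoint would then include men whose PSA says little about the drug. The cut-offs are small counts and the design has almost no spare power, so one or two such men could matter.

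**Working it through.** **Inputs.** From 12.2: null rate 0.35, alternative 0.60, 16 men in stage 1, continue with 7 or more, 27 in total, success with 13 or more. The number of men who cannot show an interpretable decline is not in the documents and is varied below.

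**Step 1: reproduce the stated design.** With a common response probability p,

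P(positive) = Σ (x = 7 to 16) Bin(x; 16, p) × P[Bin(11, p) ≥ 13 − x].

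- p = 0.35: 0.0979, against a stated 0.10.
- p = 0.60: 0.9001, against a stated 0.90.

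An exhaustive search confirms these as the minimax boundaries. Spare power is 0.0001.

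**Step 2: men who cannot respond, true rate 60% in the rest.** Keep the cut-offs. Replace 16 by 16 − k1 and 11 by 11 − k2, where k1 and k2 are the numbers of such men in each stage.

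| k1 (stage 1) | k2 (stage 2) | P(positive) |
|---|---|---|
| 0 | 0 | 0.900 |
| 1 | 0 | 0.851 |
| 0 | 1 | 0.874 |
| 1 | 1 | 0.818 |
| 2 | 0 | 0.784 |
| 0 | 2 | 0.836 |

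The last row equals the same rule with 25 assessable men in total. If instead each man independently has an assumed chance f of being unable to respond, p becomes 0.60(1 − f). P(positive) is then 0.836 at f = 5% and 0.750 at f = 10%.

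**Step 3: type I error, true rate 35% in the rest.** Let two low-PSA men meet the response definition with probability q, which the documents do not give. The ranges cover one man per stage and both in stage 1.

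| q (assumed) | Type I error |
|---|---|
| 0.1 | 0.062-0.066 |
| 0.2 | 0.076-0.078 |
| 0.35 | 0.098 |
| 0.5 | 0.119-0.122 |
| 0.8 | 0.168-0.177 |

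The error rises only if q exceeds 0.35 and falls below 0.098 otherwise.

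**Step 4: how often.** The only patient series in the documents that helps is the group's earlier fractionated antibody trial (section 2.5, part B, item i): 49 men, median PSA 44.9 ng/mL, range 1.9-766.5. Its entry rules are not given.

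- Below 1.9 ng/mL: 0 of 49. One-sided 95% upper limit 1 − 0.05^(1/49) = 5.9%.
- Below 2 ng/mL: at least 1 of 49, because the minimum was 1.9. If exactly one, the one-sided exact 95% upper limit is 9.3%.
- If the true share were an assumed 2%, the chance of at least one such man among 27 is 1 − 0.98^27 = 0.42.

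**The case against.** The strongest reply is that the problem is hypothetical. The protocol permits such men but does not show that any entered, and nobody in the 49-man series was undetectable or near 0.3 ng/mL. That stands. Every figure in steps 2 and 3 is conditional on one or two such men being present.

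A reader might infer that the stated 90% power is wrong. It is not. Section 12.2 states it for a true decline proportion of 60%, and at that rate it is correct. Men who cannot respond lower the true proportion among those counted; they do not falsify the calculation.

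A reader might also infer that low-PSA men inflate the false-positive rate. The documents do not support a direction. Section 10.2 requires confirmation and no progression, which makes chance responses less likely, and step 3 shows that the error falls if q is below 0.35. Sections 4.2 and 12.2 do not cross-refer to 10.2, but it is the only PSA response definition in the protocol.

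Finally, 2 ng/mL is not established as a baseline threshold. In 10.3, 10.5 and 10.7 it is a required increment. A man at 1.9 ng/mL must fall by 0.30 × 1.9 = 0.57 ng/mL to respond, which is not trivial. Low-PSA men also still contribute to radiographic response, radiographic progression-free survival, overall survival and CTC endpoints.

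None of this answers the case of a man with undetectable PSA. He is eligible if he progresses on imaging, he is evaluable, and he cannot meet the endpoint.

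**Conclusion.** The gap is real on the written text, and closing it is a cheap improvement; the design calculation needs no correction. If the true rate is 60% in assessable men, one man who cannot respond reduces the chance of a positive result from 0.900 to 0.85-0.87. Two reduce it to 0.78-0.82 if at least one falls in stage 1, and to 0.836 if both fall in stage 2. No direction can be given for type I error. The expected number of such men is small, on the evidence of one earlier series with unknown entry rules, and may be zero. The conclusion that the trial's result is compromised would go beyond the documents.

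**What to change.** Add to section 3.2 a minimum baseline PSA for phase II entry, and apply the same condition to the PSA-evaluable set in 12.2. An example is 2 ng/mL, chosen for consistency with the increment in 10.3, 10.5 and 10.7; the text should say that it is being adopted as a baseline threshold. The sample size and cut-offs stay as they are: if only assessable men fill the 16 and the 27, type I error remains 0.098 and power 0.900.

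Phase I men treated at the phase II dose carry over into the 16 and the 27. The study is open-label and section 6.2.4 already names the phase II total dose, so their PSA outcomes may be known. Fix the threshold without reference to those outcomes, and report the phase II result with and without any man below it. They remain in the safety analysis.

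The cost is one eligibility line and a sentence or two in 12.2. The downside is that a few low-PSA men are excluded and the result does not cover them. At 2 ng/mL this would have been at least 1 of 49 in the earlier series (upper limit about 9% if exactly one). If restricting entry is unwelcome, applying the threshold to the PSA-evaluable set alone would also close the gap.

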1.1 Primary Objectives

- Determine the Dose limiting toxicity (DLT) of fractionated dose of ¹⁷⁷Lu-PSMA-617
- Determine the cumulative maximum tolerated dose (MTD) and/or recommended phase II dose (RP2D) of ¹⁷⁷Lu-PSMA-617 in a 2-week dose-fractionation regimen

1.2 Secondary Objectives

- To assess the rate of PSA decline following fractionated ¹⁷⁷Lu-PSMA-617
- To assess radiographic response rate by RECIST 1.1 with PCWG3 modifications
- To assess biochemical and radiographic progression-free survival by PCWG3 criteria
- To assess overall survival following fractionated ¹⁷⁷Lu-PSMA-617
- To assess safety of fractionated ¹⁷⁷Lu-PSMA-617 as assessed by CTCAE 4.0
- To assess radiographic progression-free survival by PCWG3 criteria
- To assess changes in CTC count as measured by CellSearch and the rate of favorable CTC count and LDH at 12 weeks following fractionated ¹⁷⁷Lu-PSMA-617
- To examine whole body distribution of ¹⁷⁷Lu-PSMA-617
- Estimate radiation dosimetry of ¹⁷⁷Lu-PSMA-617 and correlate toxicity with radiation dosimetry

1.3 Exploratory Objectives

- Disease assessment with ⁶⁸Ga-PSMA-HBED-CC PET/CT prior to and following investigational treatment
- To assess genomic DNA repair pathways in relationship to outcome following fractionated dose ¹⁷⁷Lu-PSMA-617
- To assess patient reported outcomes using FACT-P and the Brief Pain Inventory short form
- To assess the immune effect of ¹⁷⁷Lu-PSMA-617
- To assess the reproducibility of ⁶⁸Ga-PSMA-HBED-CC PET/CT

2. BACKGROUND:

2.1. Disease

Prostate cancer (PC) is a significant health burden, with 220,800 new diagnoses and 27,540 deaths in the United States in 2015(Siegel, Miller et al. 2015). Despite advances in diagnostic technology and treatment strategies, up to 40% of patients treated with

primary therapy with curative intent will experience disease progression. Additionally, prostate cancer treatment can have a major detrimental impact on patients' quality of life, with incontinence and sexual dysfunction rates up to 18% and 90%, respectively, 15 years after therapy (Resnick, Koyama et al. 2013). The poor quality of life and prognosis of these patients has invigorated research with the goals of understanding the biological mechanisms behind PC progression and identifying novel therapeutic targets.

Localized PC is treated primarily with surgery or radiation therapy, with or without hormonal therapy, although another option for some men is active surveillance or observation, since some men will continue to be asymptomatic until death from another cause (Albertsen, Hanley et al. 1998, Albertsen, Hanley et al. 2005). Although therapy for localized disease may be successful at eradicating the disease, some patients suffer recurrence or present with advanced disease.

First line therapy for advanced PC is androgen deprivation with a mean duration of efficacy of 12-18 months, although there is a wide variation in response in this heterogeneous disease. Upon progression, the disease becomes castration-resistant and subsequently many such patients develop frank metastasis. Metastatic castration-resistant prostate cancer (mCRPC) poses a particular clinical challenge in need of additional therapeutic approaches beyond classic androgen deprivation therapies. Currently, the chemotherapy compounds docetaxel and cabazitaxel, the androgen receptor signaling inhibitor enzalutamide, CYP-17-inhibitor abiraterone, autologous cellular immuno therapy with sipuleucel-T, and the bone-seeking α -emitter ^{223}Ra have shown improved overall survival (OS) and most have demonstrated quality of life advantages as well (Petrylak, Tangen et al. 2004, Tannock, de Wit et al. 2004, de Bono, Oudard et al. 2010, Kantoff, Higano et al. 2010, Fizazi, Scher et al. 2012, Scher, Fizazi et al. 2012, Parker, Nilsson et al. 2013, Beer, Armstrong et al. 2014, Ryan, Smith et al. 2015). In all cases, however, these now established therapies become ineffective in controlling tumor progression over time (Antonarakis, Lu et al. 2014). Novel therapies are urgently needed in order to further ameliorate the course of the disease.

2.2. PSMA

In PC, the most well established, prostate-restricted, cell surface antigen yet identified is prostate specific membrane antigen (PSMA) (Horoszewicz, Kawinski et al. 1987, Israeli, Powell et al. 1993, Israeli, Powell et al. 1994, Troyer, Beckett et al. 1995, Wright, Haley et al. 1995). PSMA is a trans- membrane protein with a 707-amino-acid extracellular portion. The PSMA gene (FOLH1) is located on the short arm of

chromosome 11.

Although first thought to be entirely prostate-specific, subsequent studies have demonstrated that PSMA is also expressed by cells of the small intestine, proximal renal tubules and salivary glands(Troyer, Beckett et al. 1995). PSMA is expressed in the apical region of normal prostatic cells, the epithelium surrounding prostatic ducts(DeMarzo, Nelson et al. 2003). Dysplastic changes in the prostate result in the expression of PSMA on the luminal surface of prostatic ducts (Huang, Teh et al. 2003, Wu, Xu et al. 2012). Increasing prostate cancer stage and grade result in higher cell membrane PSMA expression (Silver, Pellicer et al. 1997, Bostwick, Pacelli et al. 1998). The eventual progression to advanced prostate cancer and castrate resistance corresponds to further increases in PSMA expression (Evans, Smith-Jones et al. 2011). PSMA expression in prostate cancer cell membranes is 100- to 1000-fold that in normal cells (Silver, Pellicer et al. 1997, Bostwick, Pacelli et al. 1998). Thus, PSMA represents a promising target for imaging and therapy of prostate cancer.

